#### **12.3.4 Concomitant medications**

All concomitant medications including prescription and over-the-counter preparations taken during the course of the study will be documented on a CRF including start and stop dates, dose, and indication for use.

#### **12.3.5 Prohibited medications**

Participants will not be allowed to receive any concomitant medication(s) that may interfere in the interpretation of data or the subject's participation in the study in the Investigator's opinion.

Metabolism of sirolimus occurs in the liver and the small intestine by the CYP3A4 family of enzymes. Thus, concomitant administration of sirolimus with other CYP3A substrates or inducers can alter the oral bioavailability of sirolimus (59). Although not a strong modulator of CYP activity, resveratrol has been reported to inhibit the activity of CYP3A4 *in vitro* and *in vivo* (60). Thus, co-administration of sirolimus and resveratrol has the potential to increase the blood levels of sirolimus or lead to an increase in the side effects of sirolimus. We will periodically monitor the sirolimus level during the study, as well as monitor closely for any adverse effects related to the study medications.

Because of the potential interaction with other drugs involving CYP3A4 metabolic pathways, strong inhibitors and strong inducers of CYP3A4 will not be allowed to be used concomitantly with the study medication. A washout period of 14 days will be required after discontinuation of the below listed medications before beginning the study medication. A list of the prohibited medications is provided in Table 4 below:

List of prohibited medications for this study
Strong CYP inducers
Barbiturates
Carbamazepine
Phenytoin
Rifampin, Rifabutin
St. John's Wort
Strong CYP inhibitors
Ketoconazole
Voriconazole
Itraconazole
Nefazodone
Clarithromycin
Erythromycin
Telithromycin
Gemfibrozil
Grapefruit juice

**Table 4:** List of prohibited medications for this study

Concomitant use of resveratrol with drugs with a narrow therapeutic range that are CYP3A, CYP1A2, CYP2D6, or CYP2C9 substrates (for example, theophylline,

tizanidine, warfarin, phenytoin, alfentanil, dihydroergotamine, ergotamine, fentanyl, pimozide, quinidine, cyclosporine, tacrolimus, thioridazine) will be prohibited from Day 1 until the end of study.

## 13. Procedures

### 13.1 Stopping rules

#### 13.1.1 Study discontinuation

The DSMB, FDA, and IRB have the authority to stop or suspend this trial at any time. This study may be suspended or closed if:

- Early stopping rules have been met
- The study objectives have been met
- The study chair/investigators believe it is not safe for the study to continue
- The DSMB suspends or closes the trial
- The FDA suspends or closes the trial

#### 13.1.2 Subject discontinuation

An intent-to-treat approach will be used. All data acquired prior to termination for the reasons outlined below will be included in the primary analysis unless patient withdraws consent. Every effort will be made to conduct a final study visit with the participant and participants will be followed clinically until, if applicable, all adverse events attributable to study drug resolve. Participants may be terminated early from the study for the following reasons:

- Withdrawal of consent
- Withdrawal by the participant
- Withdrawal by the investigator
- Intercurrent illness or event that precludes further visits to the study site or ability to evaluate disease (e.g. mental status change, large pleural effusion etc.)

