#### **13.1.4 Individual early stopping rules**

A study participant will be terminated from the study if any of the following occurs during the study:

- Recurrent or persistent resveratrol-related toxicity unresponsive to treatment in spite of dose adjustments.
- Pregnancy or failure to comply with adequate contraception
- The participant refuses to continue in the study
- Continued non-compliance
- The investigator determines that the participant should be withdrawn from the study for reasons not listed above

A subject will be considered evaluable if they receive treatment for at least 8 weeks and the relevant information collected during this period. Subjects who are withdrawn after less than 8 weeks of treatment will be considered as pre-mature discontinuation, and will be replaced by another participant.

Every effort will be made to obtain endpoint evaluations for subjects who withdraw or who discontinue prematurely from the study. The same evaluations performed at final visit will be completed at the time of termination. If withdrawal is due to inability to tolerate investigational drug or other untoward event related to investigational drug, the withdrawal will be noted in data analysis as treatment failure.

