## 15. Statistical considerations:

*Sample size determination:* As mentioned previously, the mean serum VEGF-D level prior to treatment was approximately 2,000pg/ml in both the MILES trial (12) as well as the everolimus trial (18). In both studies, treatment with mTOR inhibitors resulted in an almost 50% reduction in the serum VEGF-D levels (12, 18). Since patients in our study will be on sirolimus prior to enrolment, we estimate that the starting serum VEGF-D level in our study will be approximately 1,000pg/ml. The largest change between serial VEGF-D levels in the placebo group of MILES was 42%. Thus, VEGF-D responders in MILES trial were conservatively defined as patients in whom serum VEGF-D decreased to a value greater than 42% from its baseline (16). Accordingly, we made our power calculations based on the ability to show a greater than or equal to 42% change in serum VEGF-D levels. Assuming the correlation between the baseline and subsequent VEGF-D levels is 0.7, a sample size of 20 subjects will provide 80% power to detect a mean VEGF-D difference from baseline to post-treatment of 420pg/ml or higher with the level of significant of 0.05 and a standard deviation of 800 for the difference. Allowing for a 20% dropout rate, we expect to recruit 25 patients for our study. Sample size calculations were done using SAS version 9.4.

*Data Analysis:* The analysis will be based on an intention to treat design. All subjects that receive study drug will be included in the safety and efficacy analysis set. The primary analysis will occur after the last enrolled participant has completed the 24-week visit. All analyses will be performed using SAS version 9.4. A p-value less than 0.05 will be considered as statistically significant.

**Specific Aim #1:** To determine if combined resveratrol and sirolimus leads to reduction in serum VEGF-D compared to VEGF-D reduction on sirolimus alone. Paired t-test will be performed to detect the difference of serum VEGF-D after 24 weeks of treatment with the serum VEGF-D prior to enrolment. The response variable VEGF-D will be measured repeatedly, at baseline and at weeks 8, 16, and 24. The change from baseline to the other study time points will indicate the treatment effect with resveratrol and sirolimus.

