Initially, by using the paired t-test we will test whether these effects are statistically significant. Multivariate linear regression models will be used to assess the relationship between serum VEGF-D change and the covariates including patient's clinical or demographic factors. Linear mixed models will be performed to detect the correlation between serum VEGF-D and the covariates taking into account the correlation between repeated measurements within the same patient. A repeated measures ANOVA model and linear mixed models will be performed to compare the serum VEGF-D at follow-up visits to the baseline taking into account the correlation between repeated measurements within the same patient.

**Specific Aim #2:** To determine the safety and adverse effect profile of combined resveratrol and sirolimus in LAM. Subjects will be evaluable for safety if they have received at least one dose of the study drug. The frequency, severity and duration of all adverse events, regardless of cause, will be recorded on the case report forms. The frequency and severity of adverse events will be calculated by patient, with each patient counted once using the most severe grade experienced. The duration of adverse events

will be calculated by the number of days each event persisted. Adverse events will be tabulated by body system and by severity using the NCI Common Terminology Criteria for Adverse Events (CTCAE) v4.0, which can be obtained from the CTEP website: <http://ctep.cancer.gov/reporting/ctc.html>. Tables will be generated for all adverse events including those that are judged to be possibly, probably or definitely related to the drug. In order to assess the safety and adverse effect profile of resveratrol in LAM, we will assign a binary indicator variable to indicate a patient with or without adverse events. A multivariable logistic regression model will be used to assess of the effect of the covariates on the probability of having adverse events for patient with LAM. All interested factors will be adjusted in the logistic regression model. Model selection will be based on stepwise criterion when appropriate.

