**Home spirometry evaluation:** The spirometry values will be expressed as mean  $\pm$  SD. All spirometry maneuvers will be checked for acceptability and reproducibility as specified in the ATS/ERS criteria (38) by an expert pulmonary physiologist. The spirometry values obtained from maneuvers that do not satisfy the ATS/ERS criteria for acceptability will not be used in the primary analysis. If spirometric values meet the acceptability criteria but fail to satisfy the repeatability criteria, those values will be graded for quality, but will be used in the primary analysis. Overall compliance with weekly home spirometry will be recorded and reported as a percentage. Comparison of home spirometry and office-based spirometry values will be performed using the Bland-Altman method at baseline, and at each time frame that patients get an office-based spirometry (i.e. every 8 weeks). Rate of change of FEV1 (slope) over time will be calculated by using all available values (without imputations) in a linear mixed effects model after considering the correlation of the observations within each subject, and the time between measurements will be treated as a fixed effect. In order to analyze if the trends obtained from short-term follow up with frequent home spirometry correlate with overall disease trajectory, we will compare the rate of decline obtained after 8 weeks of home spirometry to the overall rate of decline obtained after 24 weeks of follow up. A similar analysis plan will be employed for serum VEGF-D, and other biomarkers. All statistical analyses for this study will be performed using SAS, version 9.4 (SAS Institute Cary NC).

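### The week-24 paired t-test does not carry out the plan's rule that all dosed patients and all pre-termination data enter the primary analysis, and no governing analysis is named

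*Combined protocol and SAP*

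**What the plan says.** Two statements set the principle. Section 15 (repeated in the Synopsis, Data Analysis) declares an intention-to-treat design and says: "All subjects that receive study drug will be included in the safety and efficacy analysis set". Section 13.1.2 adds: "All data acquired prior to termination for the reasons outlined below will be included in the primary analysis unless patient withdraws consent".

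The method is in Section 15, Specific Aim #1: "Paired t-test will be performed to detect the difference of serum VEGF-D after 24 weeks of treatment with the serum VEGF-D prior to enrolment". The same aim calls change from baseline at the other visits evidence of the treatment effect, says paired t-tests come first, and then lists further models: "A repeated measures ANOVA model and linear mixed models will be performed to compare the serum VEGF-D at follow-up visits to the baseline". None of these is named as the governing analysis.

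Section 13.1.4 deals with patients who leave. It asks that endpoint evaluations be sought and says: "The same evaluations performed at final visit will be completed at the time of termination". By the Visit 4 list in Section 6.3, those evaluations include VEGF-D. If the reason is intolerance or another drug-related event, "the withdrawal will be noted in data analysis as treatment failure". The same section calls a patient evaluable after 8 weeks of treatment and replaces those withdrawn earlier.

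Section 6.5 continues assessments for patients who stop the drug, so that an intention-to-treat analysis is possible.

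**The concern.** A paired t-test of week 24 against baseline can use only patients with both values. A patient who leaves after week 8 or week 16 is in the efficacy set and has data that Section 13.1.2 assigns to the primary analysis, but contributes nothing to the week-24 test. That patient appears only in the week-8 or week-16 t-tests and in the mixed models, whose standing is not stated.

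The termination sample and the treatment-failure label have no place in Section 15. The plan does not say whether a termination VEGF-D counts as the week-24 value, or what a failure label does to a test of a continuous change.

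Two analysts could therefore both follow the plan and put different patients and values into the main result. In an open-label, single-arm study of 20 to 25 patients, a handful of leavers can move the estimate visibly. A rule chosen after the data are seen would be hard to defend. If leaving is related to VEGF-D change, an estimate from week-24 pairs alone could also be biased.

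**Working it through.** **The plan's own figure.** Section 15 allows 20% dropout: 20 / (1 - 0.20) = 25 recruited, as stated. The 20 in the power calculation is therefore a number of complete pairs. The evaluable definition requires only 8 weeks of treatment, so 20 evaluable patients (Synopsis, Accrual Objective) need not be 20 week-24 pairs.

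**Inputs for an illustration.**
- From Section 15: a 420 pg/ml fall, correlation 0.7, 20 and 25 patients.
- Assumed: 20 completers fall by 420 on average by week 24. Five leavers have the same mean baseline and do not change. The correlation of 0.7, which the plan gives for baseline with later values, is applied between visits as described below.

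**Week-24 pairs only.** The 20 completers give -420.

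**Termination value substituted for week 24** (needs a termination sample from all five):
(20 × (-420) + 5 × 0) / 25 = -336. The gap is 84 pg/ml, or 84/420 = 20%.

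**Mixed model, week-24 minus baseline contrast.** With known covariance, the expected estimate is the completers' week-24 change plus the sum over earlier visits of b × (mean of all 25 - mean of completers). Here b is the coefficient of week 24 on that visit. The baseline term is zero because baseline means are equal.

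Differences between all 25 and the completers:
- Linear fall: completers -140 and -280 at weeks 8 and 16, all 25 at -112 and -224. Differences are 28 and 56.
- Fall complete by week 8: completers -420 at both, all 25 at -336. Differences are 84 and 84.

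Leavers observed at weeks 8 and 16:
- Compound symmetry, b = r/(1 + 2r) = 0.7/2.4 = 0.2917. Linear: -420 + 0.2917 × 84 = -395.5. Early: -420 + 0.2917 × 168 = -371.0.
- AR(1), 0.7 between adjacent visits, so only week 16 counts and b = 0.7. Linear: -420 + 0.7 × 56 = -380.8. Early: -420 + 0.7 × 84 = -361.2.
- Compound symmetry with other correlations: r = 0.5 gives -399.0 and -378.0; r = 0.9 gives -393.0 and -366.0.

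Leavers observed at week 8 only, compound symmetry, b = r/(1 + r) = 0.7/1.7 = 0.4118:
- Linear: -420 + 0.4118 × 28 = -408.5. Early: -420 + 0.4118 × 84 = -385.4.

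Leavers with baseline only, or completers who fall only after week 16: all differences are zero, so the mixed model returns -420, the same as the t-test.

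**No change assigned to k of five baseline-only leavers:** -420 × 20/(20 + k).

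| k | Estimate (pg/ml) |
|---|---|
| 1 | -400.0 |
| 3 | -365.2 |
| 5 | -336.0 |

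**The case against.** The documents never call the paired t-test primary. The mixed models sit under the same aim and would use every VEGF-D value collected before termination, so Aim 1 taken as a whole could honour Section 13.1.2. A leaver with a week-8 value also enters a planned paired test at week 8. This is fair, and it limits the point. The week-24 t-test is the natural reading because it comes first, matches the 24-week endpoint and fits the paired sample-size calculation. If the sponsor meant the mixed model to govern, the plan needs to say so.

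Section 13.1.4 speaks of obtaining endpoint evaluations from patients who withdraw, which suggests that termination values were meant as endpoint data. That is real evidence for substitution. Against it, Section 15 specifies VEGF-D after 24 weeks of treatment. The two pull in different directions and neither settles the matter.

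The home spirometry paragraph of Section 15 might seem to supply a missing-data rule: "by using all available values (without imputations) in a linear mixed effects model", followed by "A similar analysis plan will be employed for serum VEGF-D, and other biomarkers". The first was written for the FEV1 slope and the second follows a comparison of 8-week and 24-week slopes. Neither says what to do about a missing week-24 value in the t-test.

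The illustration is extreme. The 20% is a dropout allowance, not a forecast of missing samples, and zero change in all five leavers against 420 in completers is a hard contrast. It shows how far the reading can matter, not what will happen.

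This is also a small exploratory study, which argues for a short repair but does not remove the need for one.

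**Conclusion.** The stated rule and the stated test do not match. The governing analysis, the use of a termination VEGF-D and the meaning of treatment failure are all left open. This should be fixed. Under the stated assumptions, the reading chosen moves the estimate from -420 to as little as -336 pg/ml. A mixed model falls between -361 and -396 when leavers have week-8 and week-16 values and completers fall linearly or by week 8. These figures depend on the assumed covariance and on when the fall occurs.

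A reader might infer three stronger conclusions, and the documents support none of them:
- **That the planned estimate is biased.** Nothing shows that leaving is related to VEGF-D change, so bias is only a risk.
- **That everyone who stops resveratrol is lost.** Section 6.5 continues assessments, so the gap concerns only patients with no week-24 sample.
- **That power is lost.** The plan already allows for 20% dropout, and this point rests on no power figure.

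**What to change.** 1. Name the mixed model already listed under Aim 1 as the primary analysis: categorical visit, week-24 minus baseline contrast, all dosed patients including those later replaced (subject to the consent exception in Section 13.1.2), and all observed visits. Values collected after resveratrol is stopped are used as observed. Pre-state the covariance (for example unstructured, with compound symmetry as fallback) and use Kenward-Roger degrees of freedom. Keep the week-24 paired t-test as supportive.
2. State that a termination VEGF-D is analysed at the scheduled visit nearest its actual time and is not carried to week 24. If that visit already has a scheduled value, use the scheduled value and list the termination value.
3. Add one sensitivity analysis: a paired t-test of baseline against week 24 with no change assigned to treatment-failure patients who lack a week-24 value. This is needed because the mixed model does not correct for leavers with baseline only.
4. Use the 8-week evaluable rule for replacement only.

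Two related inconsistencies must also be reconciled. Sections 5.6 and 6.1 withdraw patients who cannot tolerate the lowest dose from the study, while Section 12.3.2 withdraws them from drug exposure, with assessments continuing under Section 6.5. Replacement in Sections 13.1.4 and 13.3 must be squared with the ceiling of 25 enrolled in Section 7.2. No clinical rule is proposed here.

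The cost is protocol and SAP wording and one extra analysis, with no new visits or samples. The downside is a little more analysis work and possibly a slightly smaller estimated effect.

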#### **6.5 Patient retention and drug compliance**

Patient retention will be encouraged in several ways. Extensive contact information will be captured for each patient, at the time of study enrollment. This will include home, work, and cellular telephone numbers and that of an emergency contact or nearest family member. Prior to each study visit, the study staff will contact the patient to remind her about the upcoming study visit. A check for the reimbursement of expenses up to \$500 will be issued after each study visit.

The study staff and physician will explain the importance of compliance with the study protocol at each patient contact. If a patient fails to comply with a study visit, the study staff will contact her by telephone. If the study staff is unsuccessful in reaching the patient, a follow up letter will be sent by overnight carrier, on two consecutive weeks, seeking follow-up.

Compliance with the protocol and drug administration will be strongly emphasized. Pill counts will be performed at visits and episodes of medication noncompliance will be recorded, including the reason for noncompliance. Patients will receive a calendar to document medication and any side effects experienced that day. If a patient wishes to withdrawal from the treatment phase of the study or has a serious adverse event (SAE) (whether related to study drugs or not), patient follow-up assessments will continue for safety monitoring and to avoid problems associated with missing data. The inclusion of such follow-up data will allow for analysis by intention-to-treat.

If a patient is withdrawn from study drug exposure for any reason, the patient will be strongly encouraged to continue with and complete the remainder of the study assessments, as scheduled.

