## 7. Stopping rules

### 7.1 Participant withdrawal criteria

Participants may be terminated early from the study for the following reasons:

- a. The participant elects to withdraw consent from all future study activities, including follow-up.
- b. The participant is “lost to follow-up” (i.e., no further follow-up is possible because attempts to reestablish contact with the participant have failed).
- c. The participant dies.
- d. The participant develops a medical condition or is started on new medication(s) not previously mentioned in the list of prohibited medications that, in the opinion of the investigator, may pose additional risks from participation in the study, may interfere with the participant’s ability to comply with study requirements or that may impact the quality of the data obtained from the study.
- e. The participant is listed for transplant and is required to stop sirolimus therapy.
- f. In the opinion of the investigator, it is not in the participant’s best medical interest to continue to participate in the study.
- g. The participant meets any of the individual stopping rules as delineated in section 13.1.

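### Section 13.1.2 removes already collected data from the primary analysis when a patient withdraws consent, which conflicts with the all-treated efficacy set and rests on an undefined withdrawal category

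*Combined protocol and SAP*

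**What the plan says.** Section 13.1.2 opens with "An intent-to-treat approach will be used" and continues: "All data acquired prior to termination for the reasons outlined below will be included in the primary analysis unless patient withdraws consent". Four reasons for early termination follow. The first is withdrawal of consent and the second is withdrawal by the participant. Neither is defined.

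Other sections bear on the same patients:

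- Section 15 (Data Analysis), repeated in the synopsis: "All subjects that receive study drug will be included in the safety and efficacy analysis set". No exception is made.
- Section 7.1(a) describes consent withdrawal this way: "The participant elects to withdraw consent from all future study activities, including follow-up". Data already held are not mentioned.
- Section 6.5 keeps assessing patients who leave the treatment phase and gives the reason: "The inclusion of such follow-up data will allow for analysis by intention-to-treat".
- Section 13.1.4 counts a patient as evaluable after at least 8 weeks of treatment, asks for final-visit evaluations at termination, and says of withdrawal for intolerance that "the withdrawal will be noted in data analysis as treatment failure". It adds another label, refusal to continue.
- Section 13.3 replaces only non-evaluable patients.
- Section 15 (Specific Aim 1) names the main test: "Paired t-test will be performed to detect the difference of serum VEGF-D after 24 weeks of treatment". It also plans tests of change at the other visits, a repeated-measures ANOVA and linear mixed models using weeks 8, 16 and 24.

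**The concern.** The efficacy set in Section 15 and the data rule in Section 13.1.2 give different answers for the same patient. Section 13.1.2 is also at odds with itself: it includes data from patients terminated for the listed reasons, and the first listed reason is the one it then excludes.

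The choice between the two rules is made after treatment, through how a departure is classified. In a single-arm, open-label trial of 25 patients, each patient is 4% of the treated group, and no control arm would offset an uneven loss. If patients who withdraw consent respond differently from those who stay, deleting their week-8 and week-16 values shifts the estimates that use those visits. Deletion also weakens the mixed model. Such a model can use a patient's earlier values to inform what is missing later, but not values that have been removed.

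**Working it through.** **1. The plan's own figure, and whether power is at issue.** Section 15 gives 20 evaluable patients for 80% power to detect 420 pg/ml, an SD of 800, a correlation of 0.7 and 20% dropout. The figure reproduces for a two-sided paired t-test at 0.05 if 800 is the SD of a single measurement:

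- SD of the difference = 800 × √(2 × (1 − 0.7)) = 619.7
- Power from the noncentral t distribution = 82.0% at n = 20 and 90.2% at n = 25
- Recruitment = 20 / 0.8 = 25

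(Section 15 words 800 as the SD of the difference. On that reading power at n = 20 is 60.6%. That is a separate matter, and nothing below depends on it.) On the reproducing reading, even five fewer pairs leave power at 82.0%. The issue is which patients are analysed, not power.

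**2. What the exclusion removes, by timing of consent withdrawal.**

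| Consent withdrawn | VEGF-D values held | Week-24 pair available if data are kept? | Removed under 13.1.2 |
|---|---|---|---|
| Between weeks 8 and 16 | baseline, week 8 | No | week-8 change |
| Between weeks 16 and 24 | baseline, weeks 8 and 16 | No | week-8 and week-16 changes |
| After the week-24 visit | all four | Yes | the week-24 pair and all earlier changes |

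In the first two rows the week-24 paired t-test is the same under either rule, unless a termination-visit value is used in place of week 24. Section 13.1.4 asks for that evaluation but does not say how it enters the analysis.

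**3. The same departure under different labels.** Take a patient who stops during week 18 because of intolerance.

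- Recorded as withdrawal by the participant, her data stay.
- Recorded as withdrawal of consent, her data leave the primary analysis.
- Under 13.1.4 she has passed 8 weeks, so she is evaluable if the relevant information was collected. Under 13.3 she is then not replaced.
- Under 13.1.4 her intolerance is also to be noted as treatment failure. Nothing says whether a failure is still counted once her data have been excluded.

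**4. Scope of the exception.** Section 13.1.2 refers to the primary analysis. Section 15 uses that term for the analysis after the last 24-week visit and again for home spirometry. The exception therefore cannot be confined with certainty to one test.

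**5. Possible size, under assumptions.** Suppose all 25 patients have a value at a given visit, *k* of them are excluded, and the mean change in those excluded is *D* pg/ml less favourable than in those kept. Then

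kept-only mean reduction − all-treated mean reduction = (k / 25) × D.

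| k | D = 210 | D = 420 |
|---|---|---|
| 1 | 8.4 | 16.8 |
| 2 | 16.8 | 33.6 |
| 3 | 25.2 | 50.4 |
| 5 | 42.0 | 84.0 |

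Against the 420 pg/ml target this is 8.4/420 = 2% to 84/420 = 20%. Both *k* and *D* are assumed. A negative *D* reverses the direction. The formula is for a simple mean at one visit; the effect on a mixed model would differ.

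**The case against.** The strongest reply is that the named primary comparison barely moves. A patient who withdraws consent before week 24 normally has no week-24 value, so she contributes no pair whichever rule holds. This stands for the paired t-test. It does not cover the other analyses planned under Specific Aim 1, termination-visit values, or consent withdrawn after week 24.

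A second reply is that the clause may respect patients who revoke permission to use their data. Section 6.3 refers to a consent and HIPAA release whose terms are not available here, so this cannot be excluded. But 13.1.2 does not say it, and 7.1(a) describes withdrawal as applying to future activities. The point limits the fix: retention must be subject to those terms.

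A third reply is that Section 13.1.4 already deals with intolerance by noting treatment failure, so these patients do not simply vanish. That is fair, but how the two rules combine is unstated.

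Three stronger readings are tempting and are not supported:

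- *Safety data are lost too.* The exception covers the primary analysis only. The safety rule, "Subjects will be evaluable for safety if they have received at least one dose of the study drug", is not contradicted.
- *Patients are removed selectively, by a classification made with results in view.* The documents give no reasons for consent withdrawal and do not say who classifies it or what that person has seen. Open-label treatment does not establish this.
- *The week-24 mean is overstated by a known amount.* One could set two withdrawers at zero change against 23 patients averaging −420, giving −420 × 23/25 = −386. That requires both withdrawers to have week-24 values and all 25 patients to be observed. Patients who leave after week 16 and before week 24 do not meet that condition.

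**Conclusion.** The concern holds as a conflict between stated rules, not as a demonstrated bias. Section 13.1.2 excludes data that the synopsis and Section 15 include, on a ground that 7.1(a) does not supply, and through a category that is not distinguished from its neighbour. Its relation to the treatment-failure rule in 13.1.4 is left open.

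The effect on the week-24 paired t-test is usually small. The rule can bias the week-8 and week-16 comparisons, the repeated-measures and mixed models, and any analysis that draws on termination-visit values or on patients who withdraw consent after week 24. The 8 to 84 pg/ml range in the working is illustrative: it assumes 1 to 5 exclusions, a 210 or 420 pg/ml less favourable response in those excluded, and complete data at the visit concerned. The actual size and direction are unknown.

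**What to change.** - In Section 13.1.2, replace the closing clause on consent withdrawal with: *Data collected up to the date on which consent is withdrawn stay in the all-treated efficacy set. No new data are collected after that date except as the patient permits. Both are subject to the terms of the signed consent and HIPAA release.*
- Repeat the rule in Section 15 and apply it to every participant-initiated withdrawal, whichever label is used.
- State how the rule combines with the treatment-failure rule in Section 13.1.4.
- Report the number of withdrawals under each label and the reasons given.

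The cost is one sentence, with its matching entries, and a check that the consent form agrees. No procedures, visits or patients are added.
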